8.2.3.2 Serious Adverse Event Reporting to the Coordinating Center

Use the University of Chicago Comprehensive Cancer Center protocol number and the protocol-specific patient ID assigned during trial registration on all reports.

All serious adverse events (as defined in [Section 8.2.3.1](#)) and all adverse events that have been specified to require expedited reporting occurring on this study require expedited reporting to the University of Chicago Comprehensive Cancer Center (UC CCC). The responsible Research Nurse or other designated individual at the treating site should report the SAE to the Study Lead Principal Investigator, the University of Chicago CRA and the CCTO by the end of the business day when s/he becomes aware of the event. Events occurring after business hours should be reported to the CCTO by 12 p.m. (noon) the next business day. Reports should be made using the 'Serious Event Report' Form. Please scan and send via email (preferred) or fax to the following:

University of Chicago Phase II CRA General:
[contact]
[contact]
[contact]

UC CCC Cancer Clinical Trials Office Quality Assurance:
[contact]

8.2.3.3 Events of Clinical Interest

Selected non-serious and serious adverse events are also known as Events of Clinical Interest

(ECI) and must be reported within 2 working days to Merck Global Safety. (Attn: Worldwide Product Safety; [contact]).

For the time period beginning when the consent form is signed until treatment allocation/randomization, any ECI, or follow up to an ECI, that occurs to any participant must be reported within 2 working days to Merck Global Safety if it causes the participant to be excluded from the trial, or is the result of a protocol-specified intervention, including but not limited to washout or discontinuation of usual therapy, diet, placebo treatment or a procedure.

For the time period beginning at treatment allocation/randomization through 90 days following cessation of treatment, or 30 days following cessation of treatment if the participant initiates new anticancer therapy, whichever is earlier, any ECI, or follow up to an ECI, whether or not related to Merck product, must be reported within 2 working days to Merck Global Safety.

Events of clinical interest for this trial include:

1. An overdose of Merck product, as defined in [Section 8.2.1](#) - Definition of an Overdose for This Protocol and Reporting of Overdose to the P.I., that is not associated with clinical symptoms or abnormal laboratory results.

2. an elevated AST or ALT lab value that is greater than or equal to 3X the upper limit of normal and an elevated total bilirubin lab value that is greater than or equal to 2X the upper limit of normal and, at the same time, an alkaline phosphatase lab value that is less than 2X the upper limit of normal, as determined by way of protocol-specified laboratory testing or unscheduled laboratory testing.*

Note: These criteria are based upon available regulatory guidance documents. The purpose of the criteria is to specify a threshold of abnormal hepatic tests that may require an additional evaluation for an underlying etiology.

8.2.4 Evaluating Adverse Events

An investigator who is a qualified physician will evaluate all adverse events according to the NCI Common Terminology for Adverse Events (CTCAE), version 5.0. Any adverse event which changes CTCAE grade over the course of a given episode will have each change of grade recorded on the adverse event case report forms/worksheets.

All adverse events regardless of CTCAE grade must also be evaluated for seriousness.

Table 6 Evaluating Adverse Events

An investigator who is a qualified physician (or nurse practitioner or physician assistant), will evaluate all adverse events as to:

V5.0 CTCAE Grading	Grade 1	Mild; asymptomatic or mild symptoms; clinical or diagnostic observations only; intervention not indicated.
	Grade 2	Moderate; minimal, local or noninvasive intervention indicated; limiting age-appropriate instrumental ADL.
	Grade 3	Severe or medically significant but not immediately life-threatening; hospitalization or prolongation of hospitalization indicated; disabling; limiting self-care ADL.
	Grade 4	Life threatening consequences; urgent intervention indicated.
	Grade 5	Death related to AE
Seriousness	
A serious adverse event is any adverse event occurring at any dose or during any use of Merck product that:
 
†Results in death; or
 
†Is life threatening; or places the participant, in the view of the investigator, at immediate risk of death from the event as it occurred (Note: This does not include an adverse event that, had it occurred in a more severe form, might have caused death.); or
 
†Results in a persistent or significant disability/incapacity (substantial disruption of one's ability to conduct normal life functions); or
 
†Results in or prolongs an existing inpatient hospitalization (hospitalization is defined as an inpatient admission, lasting >24 hours, even if the hospitalization is a precautionary measure for continued observation. (Note: Hospitalization for an elective procedure to treat a pre-existing condition that has not worsened is not a serious adverse event. A pre-existing condition is a clinical condition that is diagnosed prior to the use of a Merck product and is documented in the patient's medical history.); or
 
†Is a congenital anomaly/birth defect (in offspring of participant taking the product regardless of time to diagnosis); or
 
Is a new cancer (that is not a condition of the study) (although not serious per ICH definition, is reportable to the P.I. within 24 hours or 1 business day and to Merck within 2 working days to meet certain local requirements); or
 
Is an overdose (whether accidental or intentional). Any adverse event associated with an overdose is considered a serious adverse event for collection purposes. An overdose that is not associated with an adverse event is considered a non-serious event of clinical interest and must be reported within 24 hours to the P.I. and to Merck within 2 working days...
	

	Other important medical events that may not result in death, not be life threatening, or not require hospitalization may be considered a serious adverse event when, based upon appropriate medical judgment, the event may jeopardize the participant and may require medical or surgical intervention to prevent one of the outcomes listed previously (designated above by a †).						
Duration	Record the start and stop dates of the adverse event. If less than 1 day, indicate the appropriate length of time and units						
Action taken	Did the adverse event cause Merck product to be discontinued?						
Relationship to Merck Product	
Did Merck product cause the adverse event? The determination of the likelihood that Merck product caused the adverse event will be provided by an investigator who is a qualified physician. The investigator's signed/dated initials on the source document or worksheet that supports the causality noted on the AE form, ensures that a medically qualified assessment of causality was done. This initialed document must be retained for the required regulatory time frame. The criteria below are intended as reference guidelines to assist the investigator in assessing the likelihood of a relationship between the test drug and the adverse event based upon the available information.
 
The following components are to be used to assess the relationship between Merck product and the AE; the greater the correlation with the components and their respective elements (in number and/or intensity), the more likely Merck product caused the adverse event (AE):
 
 
 Exposure	Is there evidence that the participant was actually exposed to Merck product such as: reliable history, acceptable compliance assessment (pill count, diary, etc.), expected pharmacologic effect, or measurement of drug/metabolite in bodily specimen?	
 
 Time Course	Did the AE follow in a reasonable temporal sequence from administration of Merck product? Is the time of onset of the AE compatible with a drug-induced effect (applies to trials with investigational medicinal product)?	
 
 Likely Cause	Is the AE not reasonably explained by another etiology such as underlying disease, other drug(s)/vaccine(s), or other host or environmental factors	
 
	Exposure	Is there evidence that the participant was actually exposed to Merck product such as: reliable history, acceptable compliance assessment (pill count, diary, etc.), expected pharmacologic effect, or measurement of drug/metabolite in bodily specimen?	Time Course	Did the AE follow in a reasonable temporal sequence from administration of Merck product? Is the time of onset of the AE compatible with a drug-induced effect (applies to trials with investigational medicinal product)?	Likely Cause	Is the AE not reasonably explained by another etiology such as underlying disease, other drug(s)/vaccine(s), or other host or environmental factors
Exposure	Is there evidence that the participant was actually exposed to Merck product such as: reliable history, acceptable compliance assessment (pill count, diary, etc.), expected pharmacologic effect, or measurement of drug/metabolite in bodily specimen?						
Time Course	Did the AE follow in a reasonable temporal sequence from administration of Merck product? Is the time of onset of the AE compatible with a drug-induced effect (applies to trials with investigational medicinal product)?						
Likely Cause	Is the AE not reasonably explained by another etiology such as underlying disease, other drug(s)/vaccine(s), or other host or environmental factors						

Relationship to Merck Product (continued)	The following components are to be used to assess the relationship between the test drug and the AE: (continued)	
	Dechallenge	
Was Merck product discontinued or dose/exposure/frequency reduced?
 
If yes, did the AE resolve or improve?
 
If yes, this is a positive dechallenge. If no, this is a negative dechallenge.
 
(Note: This criterion is not applicable if: (1) the AE resulted in death or permanent disability; (2) the AE resolved/improved despite continuation of the P.I.'s product; or (3) the trial is a single-dose drug trial); or (4) P.I.'s product(s) is/are only used one time.)

	Rechallenge	
Was the participant re-exposed to Merck product in this study?
 
If yes, did the AE recur or worsen?
 
If yes, this is a positive rechallenge. If no, this is a negative rechallenge.
 
(Note: This criterion is not applicable if: (1) the initial AE resulted in death or permanent disability, or (2) the trial is a single-dose drug trial); or (3) P.I.'s product(s) is/are used only one time).
 
NOTE: IF A RECHALLENGE IS PLANNED FOR AN ADVERSE EVENT WHICH WAS SERIOUS AND WHICH MAY HAVE BEEN CAUSED BY MERCK PRODUCT, OR IF REEXPOSURE TO MERCK PRODUCT POSES ADDITIONAL POTENTIAL SIGNIFICANT RISK TO THE PARTICIPANT, THEN THE RECHALLENGE MUST BE APPROVED IN ADVANCE BY THE P.I. AS PER DOSE MODIFICATION GUIDELINES IN THE PROTOCOL.

	Consistency with Trial Treatment Profile	Is the clinical/pathological presentation of the AE consistent with previous knowledge regarding Merck product or drug class pharmacology or toxicology?
The assessment of relationship will be reported on the case report forms /worksheets by an investigator who is a qualified physician according to his/her best clinical judgment, including consideration of the above elements.		
Record one of the following	Use the following scale of criteria as guidance (not all criteria must be present to be indicative of Merck product relationship).	
Yes, there is a reasonable possibility of Merck product relationship.	There is evidence of exposure to Merck product. The temporal sequence of the AE onset relative to the administration of Merck product is reasonable. The AE is more likely explained by Merck product than by another cause.	
No, there is not a reasonable possibility of Merck product relationship	Participant did not receive the Merck product OR temporal sequence of the AE onset relative to administration of Merck product is not reasonable OR the AE is more likely explained by another cause than the Merck product. (Also entered for a participant with overdose without an associated AE.)	

8.2.5 Principal Investigator Responsibility for Reporting Adverse Events

All Adverse Events will be reported to regulatory authorities, IRB/IECs and investigators in accordance with all applicable global laws and regulations.

8.2.6 Additional Safety Considerations

Should a patient's surgery be delayed beyond the surgical window due to pembrolizumab-associated toxicity, the study would be held for a safety review by the lead investigators in order to evaluate if this event was attributable to the study intervention. If not, accrual would resume.

Safety will be assessed throughout the trial at weekly data safety monitoring meetings (DSM). Assessments will be based upon medical review of adverse events reports and the result of vital sign measurements, physical examinations, and clinical laboratory tests. The trial will be discontinued if any pembrolizumab-related deaths occur or if grade 3-4 toxicity exceeds tolerable limits by DSM review.

9.0 STATISTICAL ANALYSIS PLAN

9.1 Statistical Analysis Plan Summary

9.2 Statistical Analysis Plan

At our institution, patients with cT1b-2N0M0 GEA typically undergo surgery alone without additional therapy. Thus, we expect 100% of resected specimens to have evidence of cancer in historical controls. We hypothesize that neoadjuvant pembrolizumab will result in a pCR rate (Grade 1a+1b) of 15%. A sample size of 33 patients will provide 90% power with one-sided alpha 0.1 to detect this pCR rate using neoadjuvant pembrolizumab. More specifically, we will use an optimal, Simon two-stage design to test the null hypothesis that the Grade 1 response rate is 1% vs. the alternative that it is 15%. Fifteen patients will be enrolled in the first stage and if no complete pathological responses are observed the trial will be terminated for futility. If one or more responses are seen, an additional 18 patients will be studied for a total of 33. Two or more responses in 33 patients will indicate that the treatment is promising, whereas 0/15 or 1/33 will be considered a negative result. Patients who receive pembrolizumab but do not go to surgery will be counted as not having achieved a pCR.

We will also assess activity in the subset of patients who are PD-L1 positive. Assuming an approximate PD-L1 positivity incidence (CPS score ≥ 1) of 50% of all patients enrolled, this sample size of 16 expected PD-L1 positive patients will provide over 95% power with one-sided alpha 0.05 to detect a pCR rate (Grade 1a+1b) of 30% vs. 1% using neoadjuvant pembrolizumab in this preplanned subset. Using a higher CPS cutoff of ≥ 10 we assume 20% of patients will be PD-L1 positive based on recent data, and the sample size of 7 expected PD-

L1 positive patients will provide 67% power with one-sided alpha 0.05 to detect a pCR rate (Grade 1a+1b) of 30% vs. 1%

Complete responses (R0) will be tabulated along with an exact 90% confidence interval. DFS and OS will be estimated using the Kaplan-Meier method. Adverse events will be summarized by type, grade, and attribution to the study drug.

Chi-square tests and Spearman or Pearson correlation coefficients will be calculated to assess associations among the correlative endpoints. Comparisons of pre-treatment PD-L1 expression and other markers between responders and non-responders will be performed using two-sample t or Wilcoxon rank-sum tests. Changes in tumor markers will be analyzed using paired t or Wilcoxon signed rank tests. If the number of events is sufficient, Cox regression models will be fit to determine whether tumor markers are predictive of DFS and OS.

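### The 'over 95%' power for the PD-L1 CPS ≥ 1 subset ignores the stage 1 futility stop; with the stop it is about 90% (90–94% if PD-L1 negative patients respond at 0–10%)

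*Combined protocol and SAP*

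**What the plan says.** All the relevant text is in section 9.2 (Statistical Analysis Plan).

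- Primary design: a Simon two-stage test of 1% against 15%. The stopping rule covers all patients, whatever their PD-L1 status: "Fifteen patients will be enrolled in the first stage and if no complete pathological responses are observed the trial will be terminated for futility". Otherwise, "If one or more responses are seen, an additional 18 patients will be studied for a total of 33". Two or more responses in 33 count as promising. The stated power is 90%.
- Subset, CPS ≥ 1: half of the enrolled patients are taken to be PD-L1 positive, and on that basis the section claims that "this sample size of 16 expected PD-L1 positive patients will provide over 95% power with one-sided alpha 0.05". The rates compared are 30% and 1%, and the section describes the subset as preplanned.
- Subset, CPS ≥ 10: prevalence is taken as 20%, giving 7 expected patients and 67% power for the same 30% against 1%.

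The section gives no response rate for PD-L1 negative patients and does not say that either subset power is conditional on passing stage 1.

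**The concern.** Sixteen is about half of 33, so the subset figure presumes full accrual. Under the plan's own rule the trial can end at 15 patients with no responses, and the subset test has then failed too. A power quoted for the planned trial should count those outcomes as failures. The primary 90% does so; the subset figure appears not to. If that is right, the section reports power on two different bases without saying so. A reader would take the preplanned subset to be better protected against a missed effect than the primary test, when on the plan's own inputs it is not.

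**Working it through.** **Inputs (section 9.2).** Stage 1 has 15 patients and stage 2 has 18, 33 in total. The trial stops at 0/15. Overall alternative 15%. CPS ≥ 1 prevalence 50%. Subset rates 30% against 1%, one-sided alpha 0.05. The PD-L1 negative rate *q* is not stated. The plan's figures imply 0.15 = 0.5 × 0.30 + 0.5 × *q*, so *q* = 0; values of 5% and 10% are assumptions used to show a range. A response means Grade 1a+1b throughout, including for the stop.

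**Step 1: reproduce the stated figures.** The subset cutoff is the smallest count with exact alpha at or below 0.05 when the rate is 1%. At n = 16, a cutoff of 1 gives alpha 0.149 and a cutoff of 2 gives 0.011, so the cutoff is 2.

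- CPS ≥ 1: 1 − 0.7^16 − 16 × 0.3 × 0.7^15 = 1 − 0.0033 − 0.0228 = 0.974. This matches over 95%.
- CPS ≥ 10, n = 7, cutoff 2: 1 − 0.7^7 − 7 × 0.3 × 0.7^6 = 1 − 0.0824 − 0.2471 = 0.671. This matches 67%.

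Both are single-stage powers at a fixed subset size.

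**Step 2: let the subset size vary, without the stop.** Each enrolled patient is a PD-L1 positive responder with probability 0.5 × 0.30 = 0.15. Then P(at least 2 in 33) = 1 − 0.85^33 − 33 × 0.15 × 0.85^32 = 1 − 0.0047 − 0.0273 = 0.968. Random subset size alone costs 0.6 points. (The exact cutoff falls to 1 when the subset has 5 or fewer patients; allowing for this does not change the result to four decimals.)

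**Step 3: add the stop.** Subtract the trials that stop at 0/15 but would have had at least 2 PD-L1 positive responders among the next 18:

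power = 0.9680 − (1 − overall rate)^15 × P(at least 2 in 18),

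where P(at least 2 in 18) = 1 − 0.85^18 − 18 × 0.15 × 0.85^17 = 1 − 0.0536 − 0.1704 = 0.7759.

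| *q* | Overall rate | P(stop at 0/15) | Subset power |
|---|---|---|---|
| 0% | 15.0% | 0.0874 | 0.9680 − 0.0678 = 0.900 |
| 5% | 17.5% | 0.0558 | 0.9680 − 0.0433 = 0.925 |
| 10% | 20.0% | 0.0352 | 0.9680 − 0.0273 = 0.941 |

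A simulation of 1,000,000 trials gives 0.9002, 0.9250 and 0.9413. At *q* = 0 every response falls in the subset, so the first row is also the primary two-stage power, 0.9002. Where each of the first 15 patients responds with probability 15%, the 8.7% chance of stopping alone caps subset power at 91.3%. Power reaches 95% only when *q* is about 14%, which is 22% overall.

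**Step 4: vary the model of the subset.**

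- Exactly 16 positives among 33, divided between stages at random: 90.4%, 92.9% and 94.5% at *q* = 0%, 5% and 10%. It reaches 95% at *q* of about 12%.
- Seven positives in stage 1 and nine in stage 2: 90.8% to 94.5%.
- Eight and eight: 93.1% to 95.3%. Fixing eight positives in stage 1 lowers the chance of stopping at *q* = 0 to 0.7^8 = 5.8%.

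**Step 5: CPS ≥ 10.** Holding 15% overall gives (0.15 − 0.2 × 0.30)/0.8 = 11.25% in the other patients. With exactly 7 positives and the stop, power is 64.1%. With random subset size and the stop it is 57.1% if the cutoff stays at 2, or 68.6% if the cutoff is reset to the realised size. These fall on both sides of 67%.

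**The case against.** The strongest reply is that the sentence is true as written. It attributes the power to a sample size of 16, and 16 such patients give 97.4%. That size arises only at full accrual, so the condition can be inferred. Conditional on passing stage 1, power is 0.9002/0.9126 = 98.6%, 0.9247/0.9442 = 97.9% and 0.9407/0.9648 = 97.5% at *q* = 0%, 5% and 10%. This stands in part: the binomial calculation is right, and a conditional label would make the figure correct. But the text gives no such label, and the primary power alongside it does include the stop.

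A second reply is that 0% in PD-L1 negatives is nowhere stated. The 15% and the 30% may be separate benchmarks rather than one response model, particularly as 30% is used again for CPS ≥ 10. That is fair, and is why a range is given. At 50% prevalence, 0% is the least favourable value of *q*; the more favourable values require an overall rate above the 15% on which the trial is designed.

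A third is that the result depends on prevalence and on the division between stages. It does. At an assumed 60% prevalence, power with the stop is 94.4% at *q* = 0% and 95.8% at 5%, but the overall rate is then at least 0.6 × 0.30 = 18%. At an assumed 40% it is 82–89% over *q* of 0–10%. The eight-and-eight division passes 95% between *q* = 5% and 10%. None of these is the plan's combination of 15%, 50% and 30%.

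Last, the PD-L1 analyses are listed as exploratory in section 3.3 and no decision rule rests on the subset. This bears on the weight of the point, not on whether the figure is right.

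**Conclusion.** The concern holds, as a minor one. The stated power is correct for a single-stage test in exactly 16 patients, but the two-stage trial does not deliver it under the plan's own inputs. With the stop, power for CPS ≥ 1 is about 90%, and 90–94% if PD-L1 negatives respond at 0–10%. The chance of missing a 30% rate is 6–10% rather than under 5%. Nearly all the loss comes from the stop (96.8% to 90.0%), not from variation in subset size (97.4% to 96.8%).

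The result assumes 50% prevalence, a stated range for the PD-L1 negative rate, and a stopping rule that counts Grade 1a and 1b together. Reading the stop as Grade 1a only would make stopping more likely and lower the power further. The 67% for CPS ≥ 10 carries the same unstated condition but is not shown to be wrong. The primary test, the sample size and the stopping rule are unaffected.

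**What to change.** In section 9.2, do one of the following for CPS ≥ 1:

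- restate the power as about 90% (90–94% if PD-L1 negative patients respond at 0–10%), accounting for the stage 1 stop and taking 50% prevalence; or
- keep over 95% and label it a single-stage calculation, conditional on passing stage 1 and on full accrual of 33 with 16 PD-L1 positive patients.

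For CPS ≥ 10, keep 67% and label it conditional on full accrual and exactly 7 patients.

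The cost is one sentence or two short qualifiers. The first option makes the quoted subset power less favourable. Neither adds patients, changes the design or needs a new decision rule.

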The Cancer Genome Atlas research network recently reported the molecular characteristics of untreated gastric adenocarcinomas as part of The Cancer Genome Atlas project.[32] Gastric cancer was classified into the following four subtypes: MSI tumors (22%), EBV+ tumors (9%), tumors exhibiting chromosomal instability (CIN) (50%), and genetically stable (GS) tumors (20%). MSI has also been reported in 6.6% of untreated resected Barrett esophagus-associated EGJ AC.[33] MSI-H tumors and EBV+ tumors are thought to be sensitive to PD-1 blockade. This is due to high neoantigen levels in MSI-H tumors and due to high degree of PD-L1 positive T cell infiltration in both MSI-H and EBV+ tumors. Pembrolizumab is FDA-approved for patients with unresectable or metastatic MSI-H or dMMR of any solid tumor type, including GEA, that has progressed following prior treatment and who have no satisfactory alternatives.[6] The proportion of MSI-H tumors appears to be enriched in the early stage setting. Patients with EBV+ GC have improved survival which has been in part attributed to the associated rich CD8+ T-cell infiltrate present as part of the immune response against EBV[34-36] and increased PD-L1 and PD-L2 expression.[32] Recently reported was a patient with metastatic EBV+ esophagogastric cancer who had a durable complete response to immunotherapy.[37] It is unknown if MSI-H status or EBV positivity is predictive of response to PD-1 blockade in the neoadjuvant curative setting.

TMB quantifies mutations present in tumor cells and is currently under investigation as a potential immunotherapy biomarker in several cancer types. In patients with stage IV NSCLC, an exploratory analysis found patients with high TMB had a improved response rate and progression free survival compared to low/medium TMB, when treated with nivolumab versus platinum-based chemotherapy.[38] There was no association between level of TMB and level of tumor PD-L1 expression, however patients with PD-L1 expressions of <1% were excluded. The role of TMB as a predictive biomarker to PD-1 blockade in the early stage setting remains unknown.

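### At N=33 the plan names no exact test for categorical markers, so p-values from sparse 2x2 tables can be badly off although the tests are near nominal size on average

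*Combined protocol and SAP*

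**What the plan says.** Two sentences of section 9.2 govern the association tests.

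- The first: "Chi-square tests and Spearman or Pearson correlation coefficients will be calculated to assess associations among the correlative endpoints".
- The next compares PD-L1 expression and other pre-treatment markers between responders and non-responders by two-sample t or Wilcoxon rank-sum tests.

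Neither mentions an exact test, a rule for small expected counts, a continuity correction or a significance level. The only exact method in 9.2 is the confidence interval for R0.

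Objective 3.3b asks whether PD-L1, MSI, TMB and EBV status predict pCR, regression grade and R0. MSI and EBV are yes/no markers, and PD-L1 becomes one at the CPS cut-offs of 1 and 10.

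The counts to expect follow from the plan's own figures: 33 patients, a 15% target response rate, "Assuming an approximate PD-L1 positivity incidence (CPS score ≥ 1) of 50% of all patients enrolled", and at the higher cut-off "we assume 20% of patients will be PD-L1 positive based on recent data". Section 4.2.3.2 gives MSI 22% and EBV 9% in gastric tumors, and "MSI has also been reported in 6.6% of untreated resected Barrett esophagus-associated EGJ AC".

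**The concern.** Chi-square, t and normal-approximation Wilcoxon tests all rely on large-sample behavior. With about 5 responders and perhaps 2 to 7 marker-positive patients, a 2x2 table has only a few possible outcomes, and the p-value can be far from the true tail probability. The protocol expects MSI-high and EBV-positive tumors to be the sensitive ones, so a few responders in a rare subgroup are the signal that investigators will look for. Section 4.2.1 also lists tissue for biomarker analysis among the products of the trial. A nominally significant result from such a table could be carried into later work when an exact test would not support it.

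**Working it through.** **The plan's own figures.** The two-stage rule is 0 of 15 to stop, then at least 2 of 33.

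- Power at 15%: 1 − 0.85^15 − 15(0.15)(0.85^32) = 1 − 0.0874 − 0.0124 = 0.900, which matches the stated 90%.
- Type I error at 1%: 1 − 0.99^15 − 15(0.01)(0.99^32) = 1 − 0.8601 − 0.1087 = 0.031, inside the 0.1 limit.
- The PD-L1 subset powers also reproduce, with at least 2 responses required: 0.974 for n=16 and 0.671 for n=7.

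The plan states no expected count or p-value for the correlative tests.

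**Smallest expected count, marker by response** = 33 × prevalence × 0.15.

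| Marker | Prevalence | Positives in 33 | Smallest expected count |
|---|---|---|---|
| CPS ≥ 1 | 50% | 16.5 | 2.48 |
| MSI, gastric | 22% | 7.3 | 1.09 |
| CPS ≥ 10 | 20% | 6.6 | 0.99 |
| EBV | 9% | 3.0 | 0.45 |
| MSI, Barrett-associated EGJ | 6.6% | 2.2 | 0.33 |

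**Smallest expected count, marker by marker** = 33 × the two prevalences, under independence: CPS ≥ 1 by MSI 22%, 3.6; CPS ≥ 10 by MSI 22%, 1.45; MSI 22% by EBV, 0.65; CPS ≥ 10 by EBV, 0.59; MSI 6.6% by EBV, 0.20.

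**True size for given margins.** With m patients in one category and R in the other, the probability of a in both is C(R,a)·C(33−R,m−a)/C(33,m) under independence. Size is the sum of this over the tables that uncorrected chi-square calls significant at 0.05.

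- Margins 2 and 3: one or more in common is called significant (a=1 gives p=0.038). Size = (90 + 3)/528 = 17.6%.
- Margins 7 and 3: two or more in common is called significant (a=2 gives p=0.043). Size = (546 + 35)/5456 = 10.6%.

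These are the expected margins for MSI 6.6% by EBV (2 and 3) and for CPS ≥ 10 or MSI 22% by EBV (7 and 3). They can also arise in a marker-by-response table with 3 responders.

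**Example with 5 responders.** Three patients are marker-positive and two of them respond.

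- Chi-square = 33(2×27 − 1×3)²/(3×30×5×28) = 6.81, p=0.009.
- Fisher = (12180 + 435)/237336 = 0.053.
- Wilcoxon on the same 0/1 marker gives 0.010 and the pooled t test 0.008, so moving the comparison to the second sentence's tests does not help.

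**Average size.** Both margins are drawn as independent binomials with n=33. Tables in which a margin does not vary count as non-rejections.

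| Prevalence | Chi-square, 15% response | Fisher, 15% response | Chi-square, 10% response |
|---|---|---|---|
| 6.6% | 6.0% | 0.9% | 6.8% |
| 9% | 5.8% | 1.1% | 6.6% |
| 20% | 4.5% | 1.5% | 4.8% |
| 22% | 4.4% | 1.6% | 4.6% |
| 50% | 4.4% | 2.3% | 3.2% |

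Leaving out the tables with no variation raises the two rare-marker rows to 6.1–6.7% at 15% response and 7.2–7.8% at 10%.

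**Chance of drawing a bad table.** At 15% response, the probability that the realized margins give chi-square a true size of at least 10% is 23% at 6.6% prevalence and 18% at 9%.

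**The case against.** The strongest reply has three parts.

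1. **The wording.** A reader might infer that the plan specifies chi-square for marker-by-response tables. It does not. The chi-square sentence covers associations among the correlative endpoints, most naturally marker with marker, and the following sentence gives the response comparison to t or Wilcoxon. Chi-square reaches MSI or EBV against pCR only because it is the one categorical test named. This part stands, but it does not remove the problem: marker-by-marker tables are just as sparse, and t or Wilcoxon on a 0/1 marker behaves as chi-square does.

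2. **The extreme example.** A reader might infer that any isolated rare-marker responder would look significant, because one positive patient who responds, with 5 responders overall, gives p=0.016 against a Fisher p of 0.15. That table needs exactly one marker-positive patient in the trial (24% chance at 6.6% prevalence, 15% at 9%). Its smallest expected count is 5/33 = 0.15, and it assumes no continuity correction, on which the plan is silent; with Yates' correction p=0.32. One responder among 2 or 3 positives gives 0.156 or 0.357. The general claim is not supported.

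3. **Overall inflation.** A reader might infer a large general excess of false positives. At 5 responders and the expected marker counts, chi-square size is 1.9% (2 positive), 5.3% (3), 5.2% (7) and 4.4% (16), and the averages above are close to 5%. This stands. The averages do not help with the single table that is eventually reported, whose true size may be three times nominal or well below it.

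It is also fair that these objectives are exploratory and depend on adequate tissue and resources.

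**Conclusion.** The concern holds in a limited form. Section 9.2 names only large-sample tests for categorical markers in a trial where nearly every such 2x2 table will be sparse, and it leaves unclear which test applies to MSI and EBV against pCR. The fault is unreliable p-values in particular tables, with true size of 10.6% to 17.6% at plausible margins, and not a large average error. It is a minor point: the two-stage decision on the primary endpoint uses no association test.

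The figures assume chi-square without continuity correction and a two-sided 5% level, neither of which the plan states. They apply the prevalences in 4.2.3.2 and 9.2 to the cT1b-2N0 population; the protocol says MSI-high appears enriched in early stage, which would raise those counts. The averages take all 33 patients as enrolled and ignore early stopping. If the trial stops with no responders, there are no marker-by-response tests to run.

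**What to change.** Amend both sentences of section 9.2; changing the chi-square sentence alone would leave the response comparison as it is.

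- Use an exact test, Boschloo's or Fisher's, for all 2x2 categorical tables: marker by marker, and MSI, EBV or CPS category by pCR or R0. Boschloo's test holds its size at or below 5% and is at least as powerful as Fisher's.
- Limit t and Wilcoxon tests to continuous or ordinal markers such as CPS score and TMB.

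The change is a sentence or two of SAP text and standard software. The price is conservatism: Fisher's average size here is about 1% to 2%, so some power is lost in analyses that have little to begin with.
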